### 14.4. APPENDIX 4: ECOG PERFORMANCE STATUS

Developed by the Eastern Cooperative Oncology Group, [name], Group Chair\*

GRADE	ECOG PERFORMANCE STATUS
0	Fully active, able to carry on all pre-disease performance without restriction
1	Restricted in physically strenuous activity but able to carry out work of a light or sedentary nature, e.g. light house work, office work
2	Ambulatory and capable of all selfcare but unable to carry out any work activities; up and about more than 50% of waking hours
3	Capable of only limited selfcare; confined to bed or chair more than 50% of waking hours
4	Completely disabled; cannot carry on any selfcare; totally confined to bed or chair
5	Dead

#### 14.5. PPENDIX 5: NEW YORK HEART ASSOCIATION (NYHA)

When there is a reasonable uncertainty that the symptoms or signs are not of cardiac origin, the diagnosis should be *No heart disease*.

[figure not shown]
Functional Capacity	Objective Assessment
Class I. Subjects with cardiac disease but without resulting limitation of physical activity. Ordinary physical activity does not cause undue fatigue, palpitation, dyspnea, or anginal pain.	A. No objective evidence of cardiovascular disease.
Class II. Subjects with cardiac disease resulting in slight limitation of physical activity. They are comfortable at rest. Ordinary physical activity results in fatigue, palpitation, dyspnea, or anginal pain.	B. Objective evidence of mild cardiovascular disease.
Class III. Subjects with cardiac disease resulting in marked limitation of physical activity. They are comfortable at rest. Less than ordinary activity causes fatigue, palpitation, dyspnea, or anginal pain.	C. Objective evidence of moderate cardiovascular disease.
Class IV. Subjects with cardiac disease resulting in inability to carry on any physical activity without discomfort. Symptoms of heart failure or the anginal syndrome may be present even at rest. If any physical activity is undertaken, discomfort is increased.	D. Objective evidence of severe cardiovascular disease.

[figure not shown]
\*The Criteria Committee of the New York Heart Association. *Nomenclature and Criteria for Diagnosis of Diseases of the Heart and Great Vessels*. 9th ed. Boston, Mass: Little, Brown & Co; 1994:253-256.

[figure not shown]
# 14.6. APPENDIX 6: Effective Controception Methods

[figure not shown]
The following measures are considered to be effective conception methods:

[figure not shown]
- Diaphragm
- Intrauterine device
- Cervical cap
- Female condom
- Condom
- Spermicide

[figure not shown]

CSTONE Confidential Page 143 of 139

[figure not shown]
CSTONE Confidential Page 144 of 139

[figure not shown]
study.

> CSTONE Confidential Page 146 of 139

[figure not shown]
CSTONE Confidential Page 147 of 139

[figure not shown]

[figure not shown]

[figure not shown]
CSTONE Confidential Page 153 of 139

CSTONE Confidential Page 154 of 139

[figure not shown]

CSTONE Confidential Page 159 of 139

CSTONE Confidential Page 160 of 139

CSTONE Confidential Page 162 of 139

[figure not shown]
CSTONE Confidential Page 164 of 139

CSTONE Confidential Page 166 of 139

[figure not shown]

CStone

**CSTONE** Confidential Page 167 of 139

[figure not shown]
CSTONE Confidential Page 168 of 139

[figure not shown]

CStone

[figure not shown]

[figure not shown]
CSTONE Confidential Page 170 of 139

[figure not shown]

CSTONE Confidential Page 172 of 139

[figure not shown]

CSTONE Confidential Page 174 of 139

[figure not shown]
CSTONE Confidential Page 175 of 139

[figure not shown]

CStone

CSTONE Confidential Page 180 of 139

[figure not shown]

[figure not shown]
CSTONE Confidential Page 181 of 139

[figure not shown]
	 I		

2019
After revision: Version No.: 2.0; Version Date:
Jun 26, 2019

Page	Before	After	Rationale
	•		

[figure not shown]

[figure not shown]

CSTONE Confidential Page 186 of 139

[figure not shown]

[figure not shown]

CSTONE Confidential Page 191 of 139

	1

[figure not shown]

CSTONE Confidential Page 194 of 139

CSTONE Confidential Page 195 of 139

[figure not shown]

[figure not shown]

CStone

CSTONE Confidential Page 202 of 139

CSTONE Confidential Page 203 of 139

	1

3.	STATISTICAL METHODS.....	9
3.1	GENERAL PRINCIPLE	9
3.2	ANALYSIS SETS	9
3.2.1	Safety Analysis Set (SAS)	9
3.2.2	Efficacy Analysis Set (EAS).....	9
3.2.3	Dose-determining Set (DDS).....	9
3.2.4	Immunogenicity Analysis Set (IMAS)	10
3.2.5	Biomarker Analysis Set	10
3.3	ANALYSIS OF STUDY IMPLEMENTATION.....	10
3.3.1	Subject Distribution	10
3.3.2	Protocol Deviations	10
3.3.3	Combined Medications	10
3.4	DEMOGRAPHIC AND BASELINE CHARACTERISTICS.....	11
3.4.1	Demographics	11
3.4.2	Medical History	11
3.4.3	History of Antitumor Therapy	11
3.5	SAFETY ANALYSIS	11
3.5.1	Study Drug Exposure	11
3.5.2	Dose-Limiting Toxicity	11
3.5.3	Adverse Event	12
3.5.4	Dead	12

3.5.5	Laboratory Data	12
3.5.6	12-lead ECG	13
3.5.7	Echocardiogram	13
3.5.8	ECOG Score	13
3.5.9	Vital Signs	13
3.6	EFFICACY ANALYSIS	13
3.7	PHARMACOKINETIC AND IMMUNOGENICITY ANALYSES	14
3.7.1	Pharmacokinetic Analyses	14
3.7.2	Immunogenicity Analyses	14
3.8	BIOMARKER ANALYSES	15
3.9	Missing Values	15
3.10	Interim Analysis	15
4.	LIST OF ABBREVIATIONS	16
	APPENDIX 1: PROTOCOL SYNOPSIS	17
	APPENDIX 2: SCHEDULE OF ACTIVITIES	30
	APPENDIX 3 PROCESSING OF MISSING DATES	42

1. **BACKGROUND**

This is a multi-center, open-label, multi-dose, dose-finding and extension study for evaluating the safety, tolerance, pharmacokinetics and antitumor efficacy profiles of BLU-554 in combination with CS1001 in subjects with locally advanced or metastatic HCC.

The study consists of 2 parts, including a Part 1 (phase Ib) dose escalation and part 2 (phase II) dose expansion. Part 1 is a dose escalation study for determination of the MTD (Maximum tolerated dose) and/or RP2D (Recommended Phase II dose) of BLU-554 in the combination regimen and assess primary safety and tolerance of the combination regimen. Part 2 is a dose extension study in which preliminary evaluate the antitumor efficacy and the further evaluate the safety, tolerance, PK and immunogenicity of combination regimen.

This Statistical Analysis Plan has been written based on the CS3008 (BLU-554)-101 study protocol (version number: 2.1, version date: July 28, 2020), and describes the content and methods of statistical analysis in this study in detail.

2. **STUDY DESIGN**

2.1 **PROTOCOL SYNOPSIS**

For the protocol synopsis, see Appendix 1. For more details, see the Study Flowchart in Appendix 2.

For study indicators, see the Protocol Synopsis.

2.2 **SAMPLE SIZE DETERMINATION**

It is planned to enroll not more than 12 subjects in the phase-Ib dose-escalation study. The observed toxicity will decide the actual sample size.

According to efficacy result of BLU-554-1101 study (data cut-off date: 16 Jun 2018), ORR was 17% (11/63) for FGF19 IHC+ subjects (1st line and above) and 0 (0/38) for FGF19 IHC-subjects. ORR of PD-1/PD-L1 monotherapy was reported around 10~20% for 1st line and 2nd line HCC subjects. Based on the data above, BLU-554 in combination with CS1001 is targeting 40% ORR for FGF19 IHC+ subjects and 30% ORR for FGF19 IHC- subjects. Combining the subjects treated at RP2D in Phase Ib and those in Phase II, gating criteria in Bayesian framework are developed as the following:

Gating based on 25 FGF19 IHC+ subjects

- A non-informative ORR prior is assumed at Beta (0.45, 0.55).
- Timing - when all 25 subjects finish at least two post-baseline tumor assessments
- Go - 12 responses or more, corresponding ORR 48%, the probability of combo ORR > 40% is 0.788.
- No go - 8 (32%) responses or fewer, the probability of combo ORR<40% is 0.797.
- Evaluate - 9 (36%) to 11 (44%) responses, evaluate other endpoints, DOR, DCR, safety, etc., and additional 15 FGF19 IHC+ subjects may be enrolled for further evaluation.

Gating based on 40 FGF19 IHC+ subjects (if enrichment of 15 FGF19 IHC+ subjects as decided)

- A non-informative ORR prior is assumed at Beta (0.45, 0.55).
- Timing - when all 40 subjects finish at least two post-baseline tumor assessments
- Go - 18 responses or more, corresponding ORR 45%, the probability of combo ORR > 40% is 0.737.
- No go - 14 (35%) responses or fewer, the probability of combo ORR<40% is 0.744.
- Evaluate - 15 (37.5%) to 17 (42.5%) responses, evaluate other endpoints, DOR, DCR, etc.

Gating based on FGF19 IHC- subjects treated at RP2D in Phase Ib

- A non-informative ORR prior is assumed at Beta (0.2, 0.8).
- Timing - only conducted if at least 6 FGF19 IHC- subjects are treated at RP2D in Phase Ib, when they finish at least two post-baseline tumor assessments
- No go - 0 response, the probability of combo ORR<30% is greater than 0.99, Phase II will only include the FGF IHC+ cohort
- Evaluate - 1 response or more, the cohort of FGF IHC- subjects will be included in Phase II

Gating based on 15 FGF19 IHC- subjects

- A non-informative ORR prior is assumed at Beta (0.2, 0.8).
- Timing - when all 15 subjects finish at least two post-baseline tumor assessments
- Go - 6 responses or more, corresponding ORR 40%, the probability of combo ORR > 30% is 0.757. If the final decision for FGF19 IHC+ subjects is “go”, FGF19 IHC- subjects

may also be included in the target population of future development.

- No go - 3 (20%) responses or fewer, the probability of combo ORR<30% is 0.845. future development will not include FGF19 IHC- subjects in the target population.
- Evaluate - 4 (26.7%) to 5 (33.3%) responses, evaluate other endpoints, DOR, DCR, etc.

The sample sizes of 25 or 40 FGF19 IHC+ subjects and 15 FGF19 IHC- subjects are selected to have reasonably high probability of ORR exceeding the target when the go criteria are met or ORR being lower than the mono therapies when no-go criteria are met.

The go and no-go criteria are set up to guide future development of the combination. **They are not binding decision-making rules.**

If the actual numbers of evaluable subjects are different from those planned above, the same method will be used to calculate the posteriori probability that ORR will reach the predefined target for reference in subsequent development.

2.3 TIME OF ANALYSIS

Phase Ib: Dose Escalation

The MTD and/or RP2D of two dose levels and preliminary safety evaluation of BLU-554 in the combination regimen will be determined with the starting dose of 400 mg QD (once daily). CS1001 1,200 mg Q3W (every 3 weeks) as the fixed dose will be the RP2D in the monotherapy phase I study CS1001-101. The dose escalation part will use the BOIN design.

During the study period, an SMC consisting of the principle investigator, the CRO's representatives (CRA and other relevant person) and the sponsor's representative will be established to review the safety data, PK data, efficacy data from the study and determine the escalation dose level and dosage regimen in dose escalation study so as to determine the MTD and RP2D selected for the extension study. The SMC will also decide whether or not to include unscheduled dose levels for the study.

Phase II: Dose Expansion

The primary objective of the dose expansion phase is to further evaluate the antitumor efficacy as well as the safety, tolerability, PK and immunogenicity of the combination regimen. Subjects will be enrolled into 2 groups based on FGF19 IHC expression: Group 1 will be HCC subjects with FGF19 IHC-, approximately 15 subjects will be enrolled; Group 2 will be HCC subjects with FGF19 IHC+, approximately 25 subjects will be enrolled, approximately total 40 subjects in expansion part. Data on phase Ib evaluation at RP2D will be used as the basis to determine whether to continue to enroll subjects with FGF19 IHC- in the dose expansion phase. If the statistically pre-specified continuous evaluation range is reached, additional subjects with FGF19 IHC+ may be enrolled for further evaluation. FGF19 IHC test will be performed at central laboratory with FGF19 IHC+ defined as $\geq 1\%$ for inclusion assessment.

Archived or fresh tumor samples must be provided for FGF19 and PD-L1 IHC test which will be performed at central laboratory.

The imaging examinations of tumors shall be evaluated in accordance with RECIST v1.1. During the 1st year of the treatment, subjects will receive CT/MRI examination in the screen period and every 9 weeks (at the end of every 3 cycles). After 1 year of study, CT/MRI examinations shall be carried out once every 12 weeks (The investigator may increase the number of tumor evaluations where clinically indicated).

Subjects will be monitored for anti-tumor activity, safety, tolerability, PK profile and host immunogenicity throughout the study from the day of first administration of study drugs up to 90 days after the last administration or up to two-year treatment period of combination regimen.

2.4 OBJECTIVES AND ENDPOINTS

2.4.1 Primary Objectives and Primary Endpoints of the Study

Objectives:	Endpoints:
Primary	
Phase Ib:	

 To determine the MTD and/or RP2D of BLU-554 when being in combination with CS1001 in subject with advanced HCC. To evaluate the safety and tolerability of BLU-554 in combination with CS1001. 	
 Incidence of DLT during the administration of BLU-554 in combination with CS1001. Safety: incidence and severity of AEs and SAEs, including laboratory tests, vital signs, and ECG Tolerance: discontinuation and reduction of study drug dose
Phase II:	

 To assess the anti-tumor efficacy of BLU-554 in combination with CS1001 	
 To assess ORR based on RECIST v1.1

2.4.2 Secondary Objectives and Secondary Endpoints of the Study

Objectives:	Endpoints:
Secondary	
Phase Ib	

 To assess the pharmacokinetics (PK) profile of BLU-554 in combination with CS1001. 	Pharmacokinetic parameters include, but are not limited to: 
 When combination with BLU-554, AUC, Cmax, tmax, CLss, accumulation ratio of CS1001. When combination with CS1001, AUC, Cmax, tmax, CLss/F, accumulation ratio of BLU-554

 To preliminary assess the anti-tumor activity of BLU-554 in combination with CS1001 	
 To assess ORR, DOR, DCR, TTP, PFS and OS based on RECIST v1.1

 To assess the immunogenicity of CS1001 when administered in combination with BLU-554 	
 Occurrence of anti-CS1001 antibody

 To correlate FGF19 and PD-L1 expression level with efficacy of BLU-554 in combination with CS1001 	
 ORR, DOR, DCR, TTP, PFS and OS by FGF19 protein and PD-L1 protein level
Phase II	

 To assess the anti-tumor activity of BLU-554 in combination with CS1001. 	
 To assess DOR, DCR, TTP, PFS and OS based on RECIST v1.1

 To evaluate the safety and tolerability of BLU-554 in combination with CS1001. 	
 Safety: incidence and severity of AEs and SAEs, including laboratory tests, vital signs, and ECG Tolerance: discontinuation and reduction of study drug dose

 To assess the pharmacokinetics (PK) profile of BLU-554 in combination with CS1001. 	Pharmacokinetic parameters include, but are not limited to: 
 When combination with BLU-554, AUC, Cmax, tmax, CLss, accumulation ratio of CS1001. When combination with CS1001, AUC, Cmax, tmax, CLss/F, accumulation ratio of BLU-554.

 To assess the immunogenicity of CS1001 when administered in combination with BLU-554. 	
 Occurrence of anti-CS1001 antibody

 • To correlate FGF19 and PD-L1 expression level with efficacy of BLU-554 in combination with CS1001 	
 • ORR, DOR, DCR, TTP, PFS and OS by FGF19 protein and PD-L1 protein level
---	---

3. **STATISTICAL METHODS**

3.1 **GENERAL PRINCIPLE**

For statistical analysis, all calculations will be performed using SAS statistical analysis software version 9.4 and above.

For quantitative indicators, descriptive statistics include the number of cases, mean, standard deviation, median, minimum, and maximum, and all of which, as well as geometric mean and coefficient of variation, are included in the pharmacokinetic analysis. Unless otherwise specified, the decimal places of minimums and maximums are consistent with the original data recorded in the database. Means, medians, and geometric means have one more decimal place than the original data recorded in the database, and standard deviations and coefficients of variation have two more decimal places than the original data recorded in the database. All statistics have a maximum of four decimal places.

For categorical indicators, descriptive statistics include the number and percentage of cases. Percentages are rounded to one decimal place, and the percentage is not reported if the frequency is 0.

In the statistical test, if the P value is greater than or equal to 0.0001, 4 decimal places will be retained, and if the P value is less than 0.0001, “<.0001” will be used.

Baseline is defined as the last valid measurement or recording prior to the first study treatment.

Phase Ib data will be summarized and analyzed by dose group. Phase II data will be summarized and analyzed on an aggregate basis.

3.2 **ANALYSIS SETS**

All analysis sets will be identified prior to database lock.

3.2.1 **Safety Analysis Set (SAS)**

Safety analysis set consists of all subjects receiving at least one dose of investigational product. Subjects will be divided according to the treatment they receive.

3.2.2 **Efficacy Analysis Set (EAS)**

Efficacy analysis set consists of all subjects with measurable baseline disease who received at least one dose of investigational product.

3.2.3 **Dose-determining Set (DDS)**

Dose-determining set consists of all subjects from the safety analysis set who, in Cycle 1, meet the minimum exposure criterion and complete the follow-up on Cycle 1 Day 21 or discontinue the treatment due to DLT.

A subject is considered to have met the minimum exposure criterion if in Cycle 1 the subject has received $\geq 75\%$ of the treatment (not necessarily consecutively). Subjects who do not meet these minimum safety evaluation requirements are considered to be ineligible for the dose-determining set. Determination of the MTD uses subjects eligible for the dose-determining set.

3.2.4 Immunogenicity Analysis Set (IMAS)

Immunogenicity analysis set consists of all subjects receiving at least one dose of investigational product and having available ADA data.

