## 10.2. UMMERIES OF CONDUCT OF STUDY

10.2.1. Analysis Populations

Safety analysis set: consists of all subjects receiving at least one dose of investigational product.

**Efficacy analysis set:** consists of all subjects with measurable baseline disease who received at least one dose of investigational product. It will be the primary analysis set for efficacy in this study.

Note: Subjects who were screened but never started treatment will be listed, but not included in any efficacy analysis set. Therefore, these subjects will not be included in any of the summary tables.

**Dose-determining set:** consists of all subjects from the safety analysis set who, in Cycle 1, meet the minimum exposure criterion and complete the follow-up on Cycle 1 Day 21 or discontinue the treatment due to DLT.

A subject is considered to have met the minimum exposure criterion if in Cycle 1 the subject

has received  $\geq$ 75% of the treatment (not necessarily consecutively). Subjects who do not meet these minimum safety evaluation requirements are considered to be ineligible for the dose-determining set. Determination of the MTD uses subjects eligible for the dose-determining set.

**Pharmacokinetic analysis set**: consists of all subjects who received at least one dose of investigational product and had at least one post-baseline pharmacokinetic assessment.

**Immunogenicity analysis set**: consists of all subjects receiving at least one dose of investigational product and having available ADA data.

**Biomarker analysis set**: consists of all subjects receiving at least one dose of investigational product and having available biomarker data.

All analysis sets will be determined before the database is locked.

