3.7.2 Immunogenicity Analyses

Based on the immunogenicity analysis set, the immunogenicity assessment data will be presented according to the following categories.

- Number and percentage of subjects with positive ADA assays at baseline
- Number and percentage of subjects with at least one positive ADA assay at any time point following administration of the first dose
- Number and percentage of subjects with a positive treatment-induced ADA test at any time point after the first dose
- Number and percentage of subjects with a positive treatment-enhanced ADA test result at any time point after the first dose
- Number and percentage of subjects with a treatment-independent ADA test result at any time point after the first dose

- Number and percentage of subjects with an unevaluable ADA test result at any time point after first dose
- Overall ADA prevalence: total number and percentage of subjects with a positive treatment-induced ADA test result, a positive treatment-enhanced ADA test result, a treatment-independent ADA test result and an unevaluable ADA test result
- Overall ADA incidence: total number and percentage of subjects with a positive treatment-induced ADA test result and a positive treatment-enhanced ADA test result

Note: Treatment-induced ADA: The patient is ADA negative at baseline and ADA positive at any time after the first dose;

Treatment-enhanced ADA: The patient is ADA positive at baseline and has an enhanced ADA detection signal at any time point after the first dose (the immunogenicity titer is 4 times the baseline immunogenicity titer);

Treatment-independent ADA: The patient is ADA positive at baseline, and there is no enhancement in the ADA detection signal from the baseline titer at any time point after the first dose (the immunogenicity titer does not exceed the baseline immunogenicity titer), or the patient is ADA positive at baseline, and has all negative or deficient ADA test results after the first dose.

Unevaluable ADA: The patient is ADA deficient at baseline and ADA positive at least once at any time point after the first dose.

Those confirmed to be anti-CS1001 antibody positive were presented in the following categories.

- Number and percentage of subjects with a positive ADA neutralizing antibody (Nab) test result at baseline.
- Number and percentage of subjects with at least one positive Nab test result at any time point after the first dose.

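### Overall ADA incidence uses a denominator that keeps subjects who cannot be classified as cases, so it is slightly understated whenever any such subjects occur

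*SAP*

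**What the plan says.** **The set.** SAP 3.2.4 asks only for a dose and some ADA result: "Immunogenicity analysis set consists of all subjects receiving at least one dose of investigational product and having available ADA data". Protocol 10.2.1 gives the same definition: it "consists of all subjects receiving at least one dose of investigational product and having available ADA data". Neither asks for a post-dose result.

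**The denominator.** SAP 3.7.2 opens: "Based on the immunogenicity analysis set, the immunogenicity assessment data will be presented according to the following categories". No ADA-evaluable subset is defined there or elsewhere.

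**The numerator.** SAP 3.7.2 defines "Overall ADA incidence: total number and percentage of subjects with a positive treatment-induced ADA test result and a positive treatment-enhanced ADA test result".

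**The categories in SAP 3.7.2:**
- Treatment-induced: "The patient is ADA negative at baseline and ADA positive at any time after the first dose".
- Treatment-enhanced: positive at baseline, and "has an enhanced ADA detection signal at any time point after the first dose", specified as a titer 4 times baseline.
- Treatment-independent: includes a subject positive at baseline who "has all negative or deficient ADA test results after the first dose".
- Unevaluable: "The patient is ADA deficient at baseline and ADA positive at least once at any time point after the first dose".

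SAP 3.9 adds that missing values are not imputed. SAP 3.1 reports Phase Ib by dose group and Phase II in aggregate.

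**The concern.** An incidence should count as non-cases only subjects who had the chance to be observed as cases. Here the set is wider than the group in which the numerator can occur. A subject tested once, before the first dose, is reported in effect as free of treatment-emergent antibody, although nothing was measured after exposure.

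Occurrence of anti-CS1001 antibody is a named secondary endpoint in both phases (Protocol 3.2, SAP 2.4.2). At stake is a published incidence that is too low compared with the rate among subjects who were actually assessable. The error can only go in that direction.

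**Working it through.** **1. No figure to reproduce.** The documents give no expected ADA rate and no number of subjects lacking a post-dose sample. All counts below are therefore assumptions.

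**2. Where each type of subject lands under SAP 3.7.2.**

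| Baseline | Post-dose | Category | In numerator? | In denominator? |
|---|---|---|---|---|
| Negative | None | None listed | Cannot be | Yes |
| Positive | None | Treatment-independent | Cannot be | Yes |
| Missing | At least one positive | Unevaluable | Cannot be | Yes |
| Missing | All negative | None listed | Correctly not | Yes |

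The first two rows are the baseline-only subjects. The second row turns an absent measurement into a definite class. In the third row the SAP itself says the subject cannot be evaluated, yet nothing removes that subject from the incidence denominator.

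**3. The wording cannot be read as already meaning evaluable.** In the same list in Protocol 10.2.1, the pharmacokinetic set requires at least one post-baseline assessment and the immunogenicity set does not. The treatment-independent definition also expects subjects whose post-dose results are all missing, and keeps them.

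**4. Size.** Let x be induced plus enhanced cases, N the set size and b the baseline-only subjects, with no missing baselines for simplicity.

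- As written: x/N
- Among assessable subjects: x/(N−b)
- Ratio: (N−b)/N, so the relative understatement is 1 − (N−b)/N = b/N

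Phase II, N=40 (planned number, SAP Appendix 1), x=4 assumed:

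| b | As written | Assessable subjects | b/N |
|---|---|---|---|
| 0 | 4/40 = 10.0% | 4/40 = 10.0% | 0% |
| 1 | 4/40 = 10.0% | 4/39 = 10.3% | 2.5% |
| 4 | 4/40 = 10.0% | 4/36 = 11.1% | 10% |

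Phase Ib dose group of 6 (the minimum treated at a potential RP2D, Protocol 4.3.5), x=1 and b=1 assumed: 1/6 = 16.7% becomes 1/5 = 20.0%, with b/N = 16.7%.

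**5. Against sampling error.** Exact 95% intervals are 2.8% to 23.7% for 4/40 and 3.1% to 26.1% for 4/36. Even at b=4 the shift of 1.1 points is small beside either interval.

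**6. How many baseline-only subjects to expect.** Protocol Tables 4 and 5 show ADA sampling before dosing on Cycle 1 Day 1 and next on Cycle 2 Day 1. Protocol 7.5.2 also lists immunogenicity blood on Cycle 1 Days 2, 8 (Phase Ib only) and 15. Protocol 7.5.3 lists it at the end-of-treatment visit. If those samples are taken, a baseline-only subject has to leave early and miss all of them. On that reading b is probably small and may be zero.

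**The case against.** The strongest reply is that this hardly matters. The endpoint is reported as counts and percentages, with no test or threshold, and the go/no-go criteria rest on response rate. Counts are shown for each category and SAP 3.3.1 tabulates the analysis-set sizes. The end-of-treatment sample would catch most early leavers. The handling of baseline-positive subjects without post-dose results is written down, so it is a stated choice. All of this stands as to weight. It does not repair the denominator: a reader given x, N and the set definition still cannot recover b.

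Three stronger readings are tempting, and the documents do not support them.

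- **That subjects with no baseline and only negative post-dose results also dilute incidence.** They do not. If the missing baseline was negative, they are not treatment-induced. If it was positive, all-negative follow-up makes them treatment-independent. Either way they are true non-cases.
- **That Cycle 2 Day 1 is the first post-dose ADA sample, so every Cycle 1 dropout is lost.** Tables 4 and 5 suggest this, but the visit lists in Protocol 7.5.2 and 7.5.3 name further samples. The passages must be reconciled, and neither can be taken as settled.
- **That the loss is a material share of the 52 planned subjects (12 + 40).** No dropout figure supports that, and a pooled percentage is not a planned summary under SAP 3.1. Eligibility requires ECOG 0–1, Child-Pugh A and expected survival of at least 3 months, which argues against many subjects leaving without any later sample.

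**Conclusion.** The point holds as a small, cheap improvement. Followed literally, the SAP divides treatment-emergent ADA cases by a group that includes subjects who could not have been identified as cases, so the reported incidence is at or below the rate among assessable subjects. The relative understatement from baseline-only subjects is exactly b/N; unevaluable subjects with a missing baseline add to it. The documents fix neither number. If both are zero, nothing changes.

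The illustrated shifts of 0.3 to 1.1 points in Phase II, and 3.3 points in a dose group of 6, rest on assumed case counts and assumed b. No decision in the trial depends on them.

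**What to change.** Add one sentence to SAP 3.7.2, for example: *Percentages for treatment-induced, treatment-enhanced and overall ADA incidence use immunogenicity-set subjects with a baseline ADA result and at least one post-dose ADA result; the number excluded is reported.* Keep SAP 3.2.4 unchanged for baseline positivity, where baseline-only subjects belong.

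The cost is one sentence and no new data. The denominator becomes slightly smaller. It also drops the few subjects with no baseline and only negative post-dose results, who are true non-cases. That is acceptable because subjects with a missing baseline are then excluded whatever their post-dose result, and reporting the number excluded lets a reader judge the effect.
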